**Using fMRI-guided TMS to Increase Central
Executive Function in Older Adults
(MCI_Sub)**

NCT04176406

This document includes the study protocol and the statistical plan approved on March 1st 2020.

Study Protocol:

This experimental supplement is focused on applying TMS to a cortical network node in 30 patients diagnosed with MCI or found to be at risk for cognitive impairment (This cohort will be referred to as "MCI patients", but includes subjects with diagnosed MCI and subjects not currently diagnosed, but at risk for cognitive impairment as defined by criteria below). This blinded, sham-controlled trial will feature a mixed model 2 x 3 x 2 x 2 cross-over design, with rTMS Type (active, sham), Difficulty Level defined by accuracy (easy, medium, hard levels), Stimulation Location (Network, Activity target), and Group (healthy OAs, MCI) as factors. As such, this design reflects the fact that all subjects receive both active and sham rTMS applied to up to two different scalp locations during a WM task at up to three levels of difficulty. Study procedures are listed in **Table 3**. Thirty healthy OAs (age range: 55-80 years) and thirty MCIs (age range: 55-80 years) will participate. In the first session, which will take about 2 hours, participants will be consented and screened for the study, submit a saliva sample for genetic testing, determine TMS motor threshold, and then learn and practice the WM task. The next visit will involve a structural MRI and fMRI recorded from both groups while they perform the WM task. Cortical locations within the FPN (Network target) and DLPFC (Activity target) will be used as targets for rTMS will be chosen from an analysis of subject-specific fMRI activations from the WM task completed in this MRI Session. This session, which will last up to 3 hours, will be followed by up to four sessions of rTMS + MRI, each lasting about 3 hours. These rTMS+MRI sessions will begin ~1 week after the MRI Session, to allow for time to process the imaging data. rTMS+MRI sessions (involving active or sham rTMS and Network or Activity targets) will use coil locations and rTMS device intensities based on realistic head modeling the MRI will collect structural and resting state information.

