Working Memory task. In order to test for cognitive performance differences in response to TMS, we will rely on a validated WM task that has shown (1) reliable univariate activity in response to parametric increases in set size or load, 2) multivariate connectivity increases in response to load, and (3) reliable deficits in MCIs using similar stimuli and paradigms. Each trial comprises a set of presented words. On "rehearse" trials, individuals subvocally rehearsed a list of words across a memory delay. On "reorder" trials, individuals mentally rearranged a list of words based on the weight of the objects that the words referred to. Individuals are then probed on the correct order or position of a random word from the array. After scanning, individuals administered a surprise LTM recognition test on words processed in both conditions.

Stimuli in this experiment consisted of 504 words selected from the Medical Research Council Psycholinguistic database (http://www.psych.rl.ac.uk/MRC_Psych_Db.html). The words are 2-13 letters in length and moderate frequency, highly concrete, and highly imageable. These words were used to construct three separate lists of 168 words matched for length, frequency, concreteness, and imageability. Two of the word lists were used for the WM tasks, whereas words from the third list were used as foils for the subsequent LTM recognition test. For the two WM word lists, unique word triplets were constructed in a pseudo-randomized manner. The authors inspected the triplets to ensure that there was no ambiguity in terms of the relative referent weight or pronunciation of the words. The two WM word lists were counterbalanced between subjects and WM condition.

SALIVA SAMPLE: A saliva sample will be obtained from healthy volunteers and MCI patients in this cohort and will be used to perform APOE genetic testing, a risk marker for Alzheimer's Disease. Samples will be obtained by administration of a cheek swab and stored in a secure environment. Subject samples will be deidentified and labeled with the subject study number. Genetic testing will be performed at the Biofluids Shared Resource.

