the individualized target region, based on the cortical site with the highest computed controllability (Network target) or parametric activity (Activity target), using a MagVenture stimulator. Neuronavigation (BrainSight, Rogue Research, Canada) and a robot (SmartMove, ANT, Netherlands) will be used to optimize the targeting. Brain atrophy could also reduce TMS effectiveness because it increases the distance between scalp and the cortex but this potential confound is addressed by adjusting TMS intensity using the E-field computation. In visits 3 to 6, participants will perform the Working Memory Task while active or electrical sham stimulation is delivered using an A/P Cool-B65 coil (MagVenture, Denmark). In a stimulation trial, twenty-five pulses of 5Hz rTMS will be delivered at 100% of the effective E-field. Sham rTMS will be administered with a sham coil equipped with shielding to block magnetic field output but retain the auditory and some of the tactile aspects of active stimulation. This method reproduces the somatosensory sensations as the magnetic field stimulates scalp muscles, and produces the same acoustic artifact than the active stimulation, without inducing current in the cortex⁵⁹.

DWI Structural Connectivity. *Whole-brain tractography.* As in our prior DWI tractography work, Dipy⁶⁰ will be used to generate connectomes representing structural connections between all cortical regions in the Harvard-Oxford Atlas. For structural connection matrices, network edges are defined by the number of tractography streamlines between all nodes of the target network.

Event-related fMRI analyses, functional connectivity and graph theory measures. The Frontoparietal network (FPN) is identified by standard atlas⁶¹, and will be validated with voxelwise independent component analysis (ICA). Task-related connectivity is measured using beta-series correlations²⁰, which estimates a time-series by examining region-by-region interactions that are modulated by task conditions. SMEs for activity and connectivity will be analyzed with a Group (healthy OAs vs. MCIs) x Targeting (Network-based vs. Traditional) x Stimulation (Active vs. Sham) ANOVA using SPM⁶². All matrices are evaluated for descriptive graph-theoretical properties (including degree and controllability) using the Brain Connectivity Toolbox.

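### Word lists are counterbalanced over subjects and WM condition, but no balance over stimulation sessions, no session order and no session term is stated

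*Combined protocol and SAP*

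**What the plan says.** The Working Memory task section gives the pool: "Stimuli in this experiment consisted of 504 words selected from the Medical Research Council Psycholinguistic database", arranged as "three separate lists of 168 words matched for length, frequency, concreteness, and imageability". It continues: "Two of the word lists were used for the WM tasks", with the third list reserved as recognition foils. From the two WM lists, "unique word triplets were constructed in a pseudo-randomized manner". The only balancing statement is "The two WM word lists were counterbalanced between subjects and WM condition". A memory test follows: "After scanning, individuals administered a surprise LTM recognition test on words processed in both conditions".

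The Study Protocol section makes the design a crossover in which "all subjects receive both active and sham rTMS applied to up to two different scalp locations". It has the task practised at visit 1, performed at the MRI visit, and followed by up to four rTMS sessions. The TMS methods section confirms the repeated use: "In visits 3 to 6, participants will perform the Working Memory Task while active or electrical sham stimulation is delivered".

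The ANOVA in the section on event-related fMRI analyses has Group, Targeting and Stimulation as factors. It has no session, period or word-set term. The text describes the trial as blinded, sham-controlled and crossover, and does not say how the order of the cells is set.

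**The concern.** WM condition (rehearse or reorder) varies within a visit. Stimulation and Location vary between visits. Counterbalancing lists over WM condition therefore does nothing for the contrasts that the trial exists to estimate.

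The described stimuli (two lists, two conditions, one foil list, one surprise test) would fit a single scan. Over several visits the items must be handled in one of two ways:

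- **Reuse.** The same triplets return, and subjects can learn words and weight orders. Performance then drifts with visit number.
- **Split.** Each visit gets its own triplets. The stated matching is between lists of 168 words, not between per-visit sets, so sets may differ in difficulty.

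These are alternatives, and the text does not say which applies. In either case, if visit order or set allocation lines up with a cell across subjects, the active-sham or Network-Activity difference contains a component that is not due to stimulation. Under complete alignment no later analysis can separate the two. The Greenhouse-Geisser correction in the Analytical Rigor section deals with the covariance of repeated measures, not with a shift in means over visits.

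**Working it through.** **Pool (reproduces the plan's figure).** 3 × 168 = 504 words. WM words: 2 × 168 = 336. Triplets: 336 / 3 = 112, or 56 per list, if each word is used in one triplet.

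**Visits with the task.** MRI visit (1) + rTMS visits (up to 4) = up to 5. The items used for practice at visit 1 are not stated.

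**What each handling gives.** Reuse: each triplet is seen up to 5 times. Split over the four rTMS visits: 112 / 4 = 28 per visit, 14 per WM condition. Split over five visits: 22.4 per visit, 11.2 per condition.

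**Order effect.** Inputs: N = 60 (30 per group, Study Protocol section), two active and two sham sessions each. Assumptions: a linear gain g per session in units of the within-subject session SD, independent session errors, and no subject-by-stimulation variance.

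- Contrast per subject = mean of the active sessions minus mean of the sham sessions; SD = √(1/2 + 1/2) = 1.
- False difference = g × (mean position of active − mean position of sham).
- Sham-sham-active-active: (3+4)/2 − (1+2)/2 = 2, so 2g.
- Sham-active-sham-active: (2+4)/2 − (1+3)/2 = 1, so g.
- Active-sham-sham-active: (1+4)/2 − (2+3)/2 = 0.
- Noncentrality = false difference × √60. For g = 0.20 and both sham sessions first: 0.40 × 7.746 = 3.10.

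Rejection rates of a two-sided 5% paired t test (59 df) with no true effect:

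| Order | False difference | g = 0.05 | g = 0.10 | g = 0.20 |
|---|---|---|---|---|
| All subjects sham-sham-active-active | 2g | 12% | 33% | 86% |
| All subjects sham-active-sham-active | g | 7% | 12% | 33% |
| All subjects active-sham-sham-active | 0 | 5% | 5% | 5% |
| Randomised per subject | 0 on average | 5% | 5% | 5% |

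If both active sessions came first, the bias would have the same size and the opposite sign. The same arithmetic applies to Network-Activity.

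**Set effect, if the pool is split and all subjects share one mapping of sets to cells.** Assumptions: 75% accuracy and a between-triplet SD s of 0.05, 0.10 or 0.15 in accuracy. Each arm has 2 × 28 = 56 triplets.

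- Standard error used by the test, with binomial noise only: √(2 × 0.75 × 0.25 / 56) / √60 = 0.0106.
- SD of the active-sham set difference: s × √(2/56) = 0.0094, 0.0189, 0.0283. Adding subjects does not reduce it.
- False-positive rate = 2 × [1 − Φ(1.96 / √(1 + (set SD / SE)²))] = 14%, 34%, 49%.
- With an assumed subject-level SD of 0.10 in the paired difference added: 9%, 19%, 32%. With 0.15: 7%, 14%, 23%.

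Rotating the sets over cells evenly across subjects makes the expected set difference zero.

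**The case against.** The strongest reply is that this is silence, not a stated imbalance. A reader might infer that the active-sham contrast is biased, or that sets and order are in fact left unbalanced. The documents do not support that. They do not describe an unbalanced scheme, and the protocol refers to its Table 3 for study procedures, which is not in the text available for this check and may give an order. Randomised order alone brings the order-related false-positive rate back to about 5%. Exposure at the MRI visit precedes every stimulation cell and so is common to all of them. This stands, and it makes the bias conditional.

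The stimulus paragraph is largely in the past tense and may describe earlier use of the task. Fixed triplets also sit awkwardly with up to three difficulty levels. So 112 is the described pool, and may not be the set finally used. This stands too, but a different pool would still need an allocation over visits.

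The ANOVA cited is the imaging analysis. No full behavioural model is written, so the missing session term is a gap in both rather than a proven error in an accuracy analysis.

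A reader might also infer that the surprise recognition test supplies the SMEs in the ANOVA and loses its surprise on repetition. The documents neither define SMEs nor tie them to that test, and they do not say that the test is repeated. Only a conditional remark survives: if it is given more than once, only the first is a surprise.

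Finally, a compulsory split into five sets would leave about 11 triplets per WM condition, and 11.2 / 3 ≈ 3.7 per condition and difficulty level. That is a real cost, so splitting is not recommended here as a requirement.

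**Conclusion.** The concern holds as an omission. The stated counterbalancing does not cover the between-session contrasts, no session order is stated, and the stated ANOVA has no session term. The consequence is a risk of bias, not a demonstrated bias. It arises only if order or set allocation is unbalanced across subjects.

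For order, the false-positive rate runs from about 5% (randomised or balanced) to about 12-86% (every subject with both sham sessions first, assumed gain 0.05 to 0.20 SD per session). For a split pool with one shared mapping, it is 14-49% under binomial noise only, and 7-32% once a subject-level SD of 0.10 to 0.15 is allowed. Practice gain, between-triplet SD, 75% accuracy and the subject-level SDs are all assumptions; the documents give none of them. The upper figures are worst cases and do not describe what this trial does.

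**What to change.** 1. Within each Group, assign the four Stimulation x Location cells to visits 3-6 by a balanced sequence, either a 4 × 4 Latin square or a randomised order. With 30 per group, four sequences give 8/8/7/7.
2. State whether the triplets are reused or split over visits. That choice is left to the investigator. If they are split, rotate the sets over cells with a second square orthogonal to the first.
3. Add session number to the behavioural and imaging models, and word set if the pool is split.
4. If the recognition test is given more than once, treat only its first administration as a surprise test.

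The cost is a small allocation file and a few model degrees of freedom: one for a linear session trend (three if session is a factor), and three more for four word sets. Balance will be imperfect for subjects who complete fewer than four sessions, which the protocol's wording allows. If a balanced scheme already exists, writing it into the plan answers items 1 and 2, and only the model terms remain to be added.

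### The only active-versus-sham ANOVA has an undefined outcome (SMEs); if this means subsequent-memory effects, any rTMS effect shared by later-remembered and later-forgotten trials cancels out

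*Combined protocol and SAP*

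**What the plan says.** The section on event-related fMRI analyses, functional connectivity and graph theory measures gives the outcome and the model in one sentence. It opens "SMEs for activity and connectivity will be analyzed with a Group" factor, adds a targeting factor, and closes "x Stimulation (Active vs. Sham) ANOVA using SPM". SME is not expanded there or anywhere else, and no contrast is written for it.

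The Working Memory task section supplies the only long-term memory data: "After scanning, individuals administered a surprise LTM recognition test on words processed in both conditions". It also says that "words from the third list were used as foils for the subsequent LTM recognition test". For the working-memory trials, "unique word triplets were constructed in a pseudo-randomized manner".

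The same section gives the reason for the task: "In order to test for cognitive performance differences in response to TMS, we will rely on a validated WM task". Imaging acquisition and preprocessing says the event-related scans are meant to capture overall reactivity to that task.

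No other section writes an active-versus-sham test. The opening design paragraph lists rTMS type as a factor but names no outcome. The power analysis has group and targeting only. Analytical Rigor adds a sphericity correction, reporting standards and cross-validation, and the paragraph on sex adds a covariate.

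**The concern.** The trial's title concerns central executive function, and its task is a working-memory task. A subsequent-memory effect is a different quantity: a difference score between trials, sorted by what the person recognises later in a long-term memory test. If stimulation raises working-memory activity or connectivity on all trials alike, that score does not move. The one written imaging test of active against sham could then show nothing although the working-memory response had changed.

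There is also a problem of units. Recognition is scored word by word, while a working-memory trial holds three words. A trial with one or two of its words recognised is neither remembered nor forgotten, and the plan gives no rule for coding it.

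**Working it through.** **1. What SME is likely to mean.** Two readings are open.
- *Subsequent-memory effects.* The task includes a surprise recognition test with its own 168-word foil list, and no other analysis in the plan uses those data. The section is about event-related fMRI, where trials can be sorted by a later label.
- *Simple main effects.* These are something an ANOVA yields. In the sentence, SMEs are what is put into the ANOVA, so this reading fits less well. It is not excluded.

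The steps below apply to the first reading.

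**2. The cancellation.** Let R and F be the mean response on later-remembered and later-forgotten trials under sham, and let active rTMS add c to both. The SME is R − F under sham and (R + c) − (F + c) = R − F under active. The stimulation effect on the SME is zero whatever the size of c. If rTMS adds a to remembered and b to forgotten trials, the effect on the SME is a − b and the effect on the plain average of the two is (a + b)/2.

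**3. How much is lost.** The plan's only computed figure, average power of 0.8, does not help. It is stated for N = 80, has no active/sham factor and names no outcome. The figures below are therefore illustrations.
- From the documents: 30 + 30 = 60 people, each receiving active and sham.
- Assumed: unit SD in each of the four cells (remembered/forgotten by active/sham), common correlation ρ of 0.5 or 0.8, two-sided 5% one-sample t-test on the within-person contrast, and 5,000 simulated data sets.

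Under these assumptions the contrast for the average has variance 1 − ρ and the SME contrast has variance 4(1 − ρ). The two signal-to-noise ratios are √60(a + b)/(2√(1 − ρ)) and √60(a − b)/(2√(1 − ρ)), so the SME keeps the fraction (a − b)/(a + b) of the signal.

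| Shift a (remembered), b (forgotten), in SD | (a − b)/(a + b) | SME power, ρ = 0.5 / 0.8 | Average-activity power, ρ = 0.5 / 0.8 |
|---|---|---|---|
| 0.5, 0.5 | 0 | 0.05 / 0.05 | >0.99 / 1.00 |
| 0.5, 0.4 | 0.11 | 0.08 / 0.14 | >0.99 / 1.00 |
| 0.5, 0.25 | 0.33 | 0.27 / 0.56 | 0.98 / 1.00 |
| 0.5, 0 | 1 | 0.78 / 0.99 | 0.76 / 0.99 |

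The first row is the 5% test level, which follows from assuming an exactly uniform effect. Connectivity was not simulated. The algebra of step 2 applies to it for a shift that is equal on the scale being analysed.

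**4. Fit to triplet trials.** Two working-memory lists of 168 words give 336/3 = 112 triplets. The documents do not say how these are spread over sessions. With word hit rate h, and assuming the three words are recognised independently, the share of mixed triplets is 1 − h³ − (1 − h)³ = 3h(1 − h).
- h = 0.5: 3 × 0.5 × 0.5 = 75% mixed.
- h = 0.65: 3 × 0.65 × 0.35 = 68% mixed.
- h = 0.8: 3 × 0.8 × 0.2 = 48% mixed. Fully forgotten triplets number 112 × 0.2³ = 0.9.

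The documents give no hit rate. The mixed share exceeds half only for h between about 0.21 and 0.79.

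**5. Whether the data exist.** The opening design paragraph describes the MRI in the rTMS sessions as structural and resting-state. The ANOVA needs task activity under active and under sham. As written, the two passages do not agree.

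**The case against.** The strongest reply is that the meaning of SME is inferred. If it stands for simple main effects of activity and connectivity, nothing cancels. That stands, and the finding is conditional on the reading. The outcome would still need a definition.

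Second, a reader might infer from the first row of the table that the analysis is blind to rTMS. The documents do not support that. They do not say the effect is uniform, and an effect confined to later-remembered trials is detected about as well by the SME as by average activity.

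Third, a reader might infer that most trials cannot be classified. That depends on a hit rate the plan does not give; at 0.8 just under half are mixed, and the formula assumes independent recognition within a triplet.

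Fourth, a subsequent-memory contrast is a legitimate choice in a study that calls itself exploratory and includes a recognition test. The plan does not call this ANOVA primary, and nowhere does it commit to reporting an encoding effect as an executive-function result. So the case is for adding an outcome; it does not require demoting the SME.

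Fifth, the stated purpose of the task is cognitive performance, which is behavioural. No active-versus-sham analysis of working-memory accuracy is written either. That is a separate gap, and an added imaging outcome does not close it.

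**Conclusion.** The point holds in conditional form. It is established that the outcome of the only active-versus-sham ANOVA is an undefined abbreviation. It is likely, but not established, that it means later remembered minus later forgotten. On that reading the shared part of any rTMS effect on working-memory activity is removed by construction, and the SME keeps the fraction (a − b)/(a + b) of the signal under equal cell variances and correlations. At 60 people and a 0.5 SD shift on remembered trials, power on the SME ranges from 0.05 to 0.99 across the assumed patterns and correlations. The documents do not allow a choice within that range.

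A reader might also infer that the remedy needs only the scans already planned. That cannot be said until the plan settles whether task fMRI is acquired in the stimulation sessions. The remedy needs no more than the written ANOVA already needs.

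**What to change.** In the section on event-related fMRI analyses:
- Expand SME and write out its contrast.
- Run the group by targeting by stimulation ANOVA also on working-memory trial activity and beta-series connectivity, estimated without sorting by later recognition, and report it alongside the SME analysis.
- If the SME analysis is kept, code each trial by the number of its words later recognised (0 to 3), so that mixed triplets are used.

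Reconcile that section with the opening design paragraph on whether task fMRI is acquired under active and sham stimulation. Both the written ANOVA and the added one depend on it.

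The cost is SAP wording, one more first-level contrast and one more test to report. No data are needed beyond those the written ANOVA already requires.

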E-field Modeling. In order to determine the *intensity* of network-based targeting, we will use electric field (E-field) modeling. The BSEL lab has extensive experience with the creation of anatomically realistic E-field models of transcranial electric and magnetic stimulation in humans, which have been applied to healthy OA populations in ongoing NIH-funded projects by Co-I's [name] and [name] (U01-AG050618), using SimNIBS software⁶³. A detailed model of the TMS coil is combined with a detailed head model. Isotropic tissue conductivities are assigned to the various tissue compartments. Critically, this method will also include anisotropic conductivity in the white matter based on the DWI data. We will carry out E-field simulations over a range of coil orientations and tilts to predict maximal activation of the FPN. The target node (i.e., the node with the highest controllability, identified above) will be used as the center of a 3×3 grid for positioning the coil in simulations of the E-field corresponding to these 9 coil positions and 6 orientations (54 combinations). The simulation E-field maps will be extracted and correlated, voxel-to-voxel, with the fMRI activation and the simulation that yields the highest correlation is selected as the target coil position and orientation.

Statistical Plan:

Power analysis. Our labs have considerable experience with combining neurostimulation and neuroimaging. Through the parent award we have enrolled 85 individuals in multiday memory protocols and results from these data reflect the size of potential future TMS effects. Power calculations were therefore conducted in R software (R Development Core Team, 2016) using the repeated-measures ANOVA module. With N=80 subjects, in a mixed-effects design consisting of 4 repeated measurements per subject (2 groups x 2 TMS targeting [network-based, traditional targeting]), Cohen's $d = 0.9$ for each of the main effects, with interaction effects between 0.7-0.9, attaining an average power of 0.8 at an overall significance level of 5%.

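### No planned contrast tests active against sham stimulation at the Network target in the MCI group, which is the supplement's stated focus

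*Combined protocol and SAP*

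**What the plan says.** The opening sentence of the Study Protocol describes the supplement as "focused on applying TMS to a cortical network node in 30 patients diagnosed with MCI or found to be at risk for cognitive impairment". The same paragraph sets up a sham-controlled crossover with rTMS type, difficulty, stimulation location and group as factors. It gives the sample as "Thirty healthy OAs (age range: 55-80 years) and thirty MCIs (age range: 55-80 years) will participate" and says that "all subjects receive both active and sham rTMS applied to up to two different scalp locations".

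The section on event-related fMRI analyses, functional connectivity and graph theory measures contains the only analysis with both a response and a model. Imaging measures of activity and connectivity go into a "Group (healthy OAs vs. MCIs) x Targeting (Network-based vs. Traditional) x Stimulation (Active vs. Sham) ANOVA".

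The Power analysis paragraph gives d = 0.9 "for each of the main effects, with interaction effects between 0.7-0.9", with N = 80 and an average power of 0.8 at 5%. Its bracketed layout names group and targeting, but not active versus sham.

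Analytical Rigor adds a sphericity correction and cross-validation, and the paragraph on sex adds a gender covariate. No section names a planned contrast, a simple effect, an analysis within the MCI group, or a rule for what follows a significant interaction.

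**The concern.** The quantity that matches the stated focus is active minus sham, at the Network target, in the MCI group. The ANOVA yields Group (G), Targeting (T), Stimulation (S), GxT, GxS, TxS and GxTxS. S averages over both groups and both targets. The interactions test only whether effects differ. G, T and GxT do not involve the active-sham comparison. So the plan can be followed to the letter without estimating the effect that the supplement is about.

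Two things are at stake. An effect confined to MCI patients at the network node is spread over four terms, each less sensitive than a direct test, and none of them identifies that cell. Conversely, a significant Stimulation main effect can arise with no effect in MCI at all.

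**Working it through.** **The plan's own figure.** The stated average power of 0.8 cannot be reproduced uniquely, because the within-subject correlation and the definition of d for an interaction are not given. Treating the 80 subjects as a between-subject 2 x 2 with 20 per cell comes close. Main effects at d = 0.9 have power 0.978 and an interaction at d = 0.8 has 0.423, so the average is (0.978 + 0.978 + 0.423)/3 = 0.793. Mixed repeated-measures layouts at N = 80 give averages of 0.86 to 1.00. None of these is the power of active versus sham in MCI patients.

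**Inputs.** From the documents: 30 + 30 subjects, two targets, active and sham within subject, 5% significance. Assumed: complete data, one scalar outcome, two-sided tests. The unit is the SD of one person's active-minus-sham difference at one target, and rho is the correlation of that difference between targets. The main case takes d = 0.6 and rho = 0.3.

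**The target as a combination of terms.** Define S as the mean difference over groups and targets, GxS as MCI minus healthy, TxS as Network minus Activity, and GxTxS as the difference of those differences. Then the effect in MCI at Network = S + GxS/2 + TxS/2 + GxTxS/4. If it equals d and the other three cells are zero, the pieces are d/4 + d/4 + d/4 + d/4 = d. The contrast can be estimated from the planned data, but no single term equals it.

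**Power when the effect is confined to MCI at Network (d = 0.6, rho = 0.3).**

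| Test | Expected value | Standard error | Ratio | df | Power |
|---|---|---|---|---|---|
| S | d/4 = 0.15 | sqrt[((1+rho)/2)/60] = 0.104 | 1.44 | 58 | 29% |
| GxS | d/2 = 0.30 | sqrt[((1+rho)/2)(2/30)] = 0.208 | 1.44 | 58 | 29% |
| TxS | d/2 = 0.30 | sqrt[2(1-rho)/60] = 0.153 | 1.96 | 58 | 49% |
| GxTxS | d = 0.60 | sqrt[2(1-rho)(2/30)] = 0.306 | 1.96 | 58 | 49% |
| Direct contrast | d = 0.60 | 1/sqrt(30) = 0.183 | 3.29 | 29 | 89% |

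At rho = 0 each of the four terms has 37%. At rho = 0.5, S and GxS have 26% and TxS and GxTxS have 63%. The direct contrast does not depend on rho.

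**The four terms as a set.** In simulation (40,000 trials, same setting) at least one is significant in 87% of trials. Under the null the figure is about 18%, which agrees with 1 - 0.95^4 = 0.185.

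**Stimulation significant with no effect in MCI.** Let the effect d exist only in healthy adults, equally at both targets, with rho = 0.3. S and GxS then have the same ratio: (d/2)/0.104 = d/0.208. Simulated frequency of a significant S with a non-significant GxS:

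- d = 0.3: 21%
- d = 0.4: 24%, about half of the 47% of trials in which S is significant
- d = 0.5: 22%
- d = 0.6: 15%
- d = 0.7: 8%
- d = 0.9: 1%

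**What 30 patients can detect.** A paired test with 29 df has 80% power at two-sided 5% when d x sqrt(30) = 2.90, so d = 2.90/5.477 = 0.53. At 2.5% the value is 0.59.

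**The case against.** The strongest reply is that the ANOVA does not let such an effect slip by. In the scenario above at least one Stimulation term is significant in 87% of trials, close to the 89% of the direct contrast. At a paired d of 0.9 and rho = 0.3, TxS and GxTxS each reach 83% and at least one term is significant in over 99%. The one-cell scenario is also unfavourable to the ANOVA. With d = 0.6 in MCI at both targets, S and GxS have 81% each. With d = 0.6 at Network in both groups, TxS has 97% and S has 81%. This stands. A reader might infer that an MCI effect would mostly be missed, and the documents do not support that. What remains is localisation: a significant term does not say that the effect lies in MCI at the network node, and counting any of four carries the false-positive rate of about 18%.

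Second, a reader might infer that the plan will credit a pooled effect to MCI. No section says so. Group x Stimulation is in the model and would flag a healthy-only effect of 0.6 at both targets in 81% of trials. It is a weaker guard against a merely smaller MCI effect. With 0.53 in healthy adults and half that in MCI at both targets (rho = 0), S is significant without GxS in about 70% of trials.

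Third, the focus sentence does not declare a primary estimand, and group and location are design factors, so the questions may be meant as comparative. The paragraph on sex also calls the study exploratory. Both are fair and limit the severity. They do not explain why the effect named as the focus should go without a planned estimate.

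Fourth, the ANOVA concerns imaging measures. Neither it nor a contrast added to it would show clinical benefit. This stands, and is why the fix extends to task performance.

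**Conclusion.** The point holds as a gap between stated focus and written analysis. None of the seven ANOVA effects is active minus sham at the Network target in MCI, and no contrast supplies it. For a moderate effect confined to that cell, a single term has 29% to 49% power where the direct contrast has 89%. The gap narrows for larger effects and for effects shared across groups or targets. A Stimulation main effect alone cannot establish an effect in MCI: it appears without Group x Stimulation in about 15% to 24% of trials when only healthy adults respond at 0.3 to 0.6. That is a risk of interpretation which the plan leaves open, not one it commits.

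The figures rest on assumed d and rho, complete data and one scalar outcome; voxelwise correction was not modelled. A reader might also infer that the pooled error term would be invalid for the MCI group. That needs a ratio of group SDs, which the documents do not give, so it forms no part of the conclusion. The change should be made, but the ANOVA itself need not be replaced.

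**What to change.** Keep the ANOVA. In the event-related fMRI analysis section, add one planned contrast: active minus sham at the Network target within the MCI group, as a paired within-group comparison, reported with a 95% CI whatever the interaction tests show. Apply the same contrast to working-memory performance, since the Working Memory task section gives that as the purpose of the task. State that a Stimulation main effect alone will not be reported as an effect in MCI.

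In the Power analysis paragraph, state what this contrast can detect: paired d of about 0.53 with 80% power at two-sided 5%, if all 30 MCI patients complete both Network sessions and before any voxelwise correction. Because the protocol allows up to two locations rather than requiring both, this is a best case.

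The same contrast at the Activity target, with Holm over the two, is optional. At the 2.5% step, power at d = 0.6 is 82% and the detectable effect is 0.59.

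The cost is plan wording and contrast weights, with no new data or procedures. The downsides are one more planned test on each outcome, 29 instead of 58 error degrees of freedom, and an explicit detectable effect for the MCI group.
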